4.2 Secondary Endpoints

Protective Efficacy:

1. *P. falciparum* blood stage infection defined as time to first positive blood smear (detection of at least two *P. falciparum* parasites by microscopic examination of 0.5 μ L) starting immediately following 3rd injection. (Main Phase)
2. *P. falciparum* blood stage infection defined as time to first positive blood smear (detection of at least 2 *P. falciparum* parasites by microscopic examination of 0.5 μ L) starting immediately following 4th injection (Booster Phase).

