5.5.1 Indications for Deferral of Vaccination

If any of the following AEs occurs at the time of the scheduled injection (vaccination with PfSPZ Vaccine or normal saline), the subject may be either vaccinated at a later date within the allowable visit window as specified in the protocol or withdrawn at the discretion of the Investigator:

- Oral temperature $>37.5^{\circ}\text{C}$ at the time of injection will warrant deferral of injection until fever resolves (within protocol-defined window).
- Any other condition that in the opinion of the Investigator poses a threat to the individual if vaccinated or that may complicate interpretation of the safety of vaccine following vaccination.

Such individual(s) will be followed in the clinic until the symptoms resolve or the window for injection expires. No further injections will be performed if the subject does not recover (temperature $\leq 37.5^{\circ}\text{C}$ and/or lack of symptoms) or develops a chronic condition deemed unsafe for future injections. The subject will be monitored for safety and immunogenicity for at least 3 months after their last injection (PfSPZ vaccine or normal saline) unless the subject has withdrawn consent. If the subject does not receive any further vaccinations, then some scheduled safety blood draws may not be performed at the discretion of the PI. Blood draws scheduled to measure immune response may be obtained if possible.

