7.2 Assignment of Groups

Enrollment **in the main phase** occurs with collection of baseline study samples on study Day -14. Randomization will occur prior to enrollment, prior to or on study Day -14. Randomization of the subjects in Arm 1 and 3a will occur first as these subjects will be enrolled first. Randomization of Arm 2 and 3b will occur together later prior to enrollment. If a subject was randomized into group 1 or 3a but was not vaccinated, they may be randomized into groups 2 and 3b if still eligible.

If a subject withdraws from the study after randomization, they can be replaced by another subject at random if withdrawal happens prior to receipt of first vaccination. Once a subject has received their first vaccination, they cannot be replaced.

For the booster phase, enrollment will occur at the receipt of the first dose of artemether/lumefantrine prior to vaccination. Enrolled subjects cannot be replaced.

During the study, the list linking randomization numbers to study product (PfSPZ Vaccine or control) will be made available only to the study statistician and associated team members, pharmacy team/syringe preparers (at the start of the study), independent safety monitor (if needed to review as outlined in **Section 11.15.2**), and DSMB chair (if needed for closed session unblinded review). On vaccination days, the vaccines associated with each randomization number will be obtained from the pharmacist.

To ensure proper identification of study subjects, following subject enrollment all subjects will receive an identification card with their photo on it to present at the clinic with each study visit.

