11.13 Withdrawal of an Individual Subject

A subject will not be considered to have completed the trial if any of the following reasons apply:

1. *Research terminated by Sponsor or Investigator* – applies to the situation where the entire study is terminated by the sponsor or investigator, or other regulatory authority for any reason.
2. *Withdrawal of consent* – applies to a subject who withdraws consent to participate in the study for any reason.
3. *Noncompliant with protocol* – applies to a subject who does not comply with protocol-specific visits or evaluations, on a consistent basis, such that adequate follow-up is not possible, and the subject's safety would be compromised by continuing in the trial. This also applies to a subject who is lost to follow-up and is not reachable by telephone or other means of communication and cannot be located.
4. *Completed follow up after developing an AE* – applies to a subject who is withdrawn from study due to an AE, serious or otherwise. Any grade 3 or greater AE that is assessed as possibly, probably, or definitely related to vaccination, PfSPZ Vaccine or placebo (other than local reactions lasting <72 hours, or systemic reactions lasting <48 hours) will result in withdrawal of the subject from further vaccinations. Subjects may also be withdrawn for any AE that would cause continued participation in the study to not be in the best interest of the subject, as per the investigator's judgment. Any subject who will not receive any further vaccination because of an AE related to study agent will be followed for safety until at least resolution of that AE and will be encouraged to remain in the safety evaluation for the duration of the study.
5. *Other* – is used when previous categories do not apply and a written explanation is required.

If a subject withdraws or is withdrawn prior to completion of the study, the reason for this decision will be recorded in the source documents and CRFs. Any subject who has received at least one dose of vaccine will be encouraged to remain in the safety evaluation for the duration of the study. The subject's data will be included in the safety and immunogenicity analysis. If a subject fails to complete all planned vaccinations because of an AE or SAE, the subject will be followed until resolution or stabilization of the event. If a subject withdraws, the investigator will make a reasonable effort to determine the reason.

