13.1.2 Vaccine efficacy analysis

Primary efficacy analysis will be based on time to infection, which is defined as the time to the first positive blood smear. Arms will be compared by logrank test for interval-censored data (using the interval package in R). VE will be estimated assuming a Weibull model and allowing for interval censoring and stratification by village (survival package in R).

The proportions of infection will be also compared across arms by the exact binomial test, or the Exact Cochran-Mantel-Haenszel test stratifying on village if needed (using the mantelhaen.test in R with the exact option set to true, this is a conditional exact test). Subjects that are censored prior to the last day of planned follow up will be removed from the analysis and censoring will be assumed to be completely at random. A sensitivity analysis may be performed where all censored subjects are treated as either cases or non-cases in either arm.

Under either of these analyses, we will perform an ITT and a per-protocol analysis. Under the per-protocol analysis, subjects that drop out prior to receiving the full number of vaccinations will not be included in the analysis.

The same efficacy analyses will be performed at the end of the main phase and the end of the booster phase.

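### The supporting proportion-of-infection analysis deletes only uninfected leavers, which biases vaccine efficacy slightly toward zero even under completely random dropout

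*Combined protocol and SAP*

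**What the plan says.** Section 13.1.2 plans two efficacy analyses. The primary one is time to first positive smear, with an interval-censored logrank test and a Weibull model for VE. The second compares the proportions infected by an exact test. For this second analysis, "Subjects that are censored prior to the last day of planned follow up will be removed from the analysis". The accompanying assumption about those who leave is that "censoring will be assumed to be completely at random". As a check, "A sensitivity analysis may be performed where all censored subjects are treated as either cases or non-cases in either arm".

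On analysis sets, "Under either of these analyses, we will perform an ITT and a per-protocol analysis". Per-protocol leaves out those who drop out before full vaccination; ITT for efficacy is not defined further. Section 4.2 counts infection time as "starting immediately following 3rd injection" in the main phase, and from the 4th injection in the booster phase. No origin is given for a randomised subject who misses that injection.

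**The concern.** Whether a leaver is deleted depends on the outcome. A subject infected in week 4 who then leaves stays in the table as a case. A subject still uninfected at week 20 who leaves is removed from numerator and denominator. The missing-completely-at-random assumption does not repair this, because the selection comes from the rule and not from the reasons for leaving. Non-cases are lost, cases are kept, and the arm with more uninfected people loses more of them. If the vaccine works, that is the vaccine arm.

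At stake is the proportion VE that will be reported beside the time-to-infection VE in both phases. It would carry a small built-in error, and its size and sign would depend on how many subjects leave each arm.

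**Working it through.** **Inputs.** Background infection 0.7, VE 45% and annual dropout of 15% to 28% are from Section 13.2. Follow-up is 182 days after the 4th injection (Appendix A). The main phase agrees: with the first injection on Day 1, the 3rd falls on Day 113 or Day 29, and 295 - 113 = 211 - 29 = 182 (final days from Section 4.4).

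**The plan's own figure.** Table 8 gives 88% power for 50 per arm, background 0.7, VE 45%. Take VE as a risk reduction: p1 = 0.7 × 0.55 = 0.385. Then HR = ln(0.615)/ln(0.3) = 0.404 and expected events are 50 × (0.70 + 0.385) = 54.25. Freedman's formula gives Φ(√54.25 × 0.596/1.404 - 1.96) = 87.9%. Two-sided alpha 0.05 and 1:1 allocation are assumed. The plan's 45% therefore behaves as a risk reduction, and I use that case as well as HR 0.55.

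**Bias formula.** Assume constant infection hazard and dropout independent of infection. Let h = -ln(1 - p) and g = -ln(1 - d) × 182/365.
- Infected before leaving: a = h/(h + g) × (1 - e^-(h+g)).
- Completes uninfected: c = e^-(h+g).
- Deleted: 1 - a - c.
- Proportion infected among those kept: a/(a + c).

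For d = 15%, g = 0.0810; for d = 28%, g = 0.1638. Control h = 1.204. Vaccine h = 0.486 at p1 = 0.385, and 0.662 at HR 0.55 (p1 = 0.484).

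Worked case, 28% per year, VE 45%:
- Control: a = 0.6561, c = 0.2547, kept proportion 0.7204, deleted 8.9%.
- Vaccine: a = 0.3575, c = 0.5221, kept proportion 0.4064, deleted 12.0%.
- Estimated VE = 1 - 0.4064/0.7204 = 43.6%.

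| Dropout (control / vaccine) | True VE 45.0% | True VE 30.8% (HR 0.55) |
|---|---|---|
| 15% / 15% per year, 182 days | 44.3% | 30.2% |
| 28% / 28% per year, 182 days | 43.6% | 29.6% |
| 15% / 28% per year, 182 days | 42.8% | 28.6% |
| 28% / 15% per year, 182 days | 45.1% | 31.2% |
| 15% / 15%, all within follow-up | 43.6% | 29.6% |
| 28% / 28%, all within follow-up | 42.1% | 28.3% |
| 15% / 28%, all within follow-up | 40.5% | 26.3% |
| 28% / 15%, all within follow-up | 45.1% | 31.5% |

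The last four rows set g = -ln(1 - d). At background 0.6 the unequal cases within follow-up run from -4.7 points (34.0% to 29.3%, HR 0.55) to +1.5 points (30.0% to 31.5%, VE 30% on the risk scale).

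**Timing of infection.** If all infections came at the very end of follow-up, the bias would vanish. If all came at the start, the kept proportion would be p/[p + (1 - p)e^-g]. At 28% per year that is 0.700/0.955 = 0.733 against 0.385/0.907 = 0.424, so VE 42.1%, a bias of 2.9 points.

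**The optional sensitivity analysis.** With 15% leaving each arm within follow-up and true VE 45%, counting all censored subjects as cases gives 35.9%, and as non-cases 45.5%. Opposite assignments in the two arms give 27.3% to 52.0%. At 28% the range is 9.5% to 57.6%. These are bounds and do not correct the estimate.

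**Subjects without a time origin.** Table 4 gives 105 per schedule pair. Table 5 shows 101 and 103 received the 3rd injection: 4 + 2 = 6 of 210 (2.9%) did not.

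**The case against.** The strongest reply is that the rule touches only a supporting analysis of a secondary endpoint. The primary interval-censored analysis keeps every censored subject until departure. That stands. With equal dropout the error is also small and conservative. Losses after the last dose were low in the earlier Mali trials: 88 to 86 (Section 1.4.3.1), and 57 + 55 = 112 receiving three doses to 109 evaluable (Section 1.4.3.3.2). With 3% loss within follow-up the bias is only 0.2 to 0.3 points. That stands too, although Section 13.2 itself plans for far more loss. The case/non-case check is a weaker defence: it is optional, its scheme is open, and it only bounds.

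A reader might infer more than the documents support:
- *That ITT equals per-protocol.* The plan leaves ITT undefined but states no exclusion. The earlier Mali trial also started its clock after the third dose, yet reported time-to-infection VE of 39% by ITT and 51% per protocol (Section 1.4.3.3.2).
- *That subjects who stop injections have no smears.* Section 5.5.1 says "The subject will be monitored for safety and immunogenicity for at least 3 months after their last injection", and Section 11.13 that a withdrawn subject's "data will be included in the safety and immunogenicity analysis". The first is a minimum, and neither stops smears or bars efficacy use. Sections 6.5, 11.4.4 and 15.7 keep pregnant subjects on malaria evaluation after dosing stops.
- *That subjects are counted twice.* Section 7.2 says of subjects randomised to Arms 1 or 3a but never vaccinated that "they may be randomized into groups 2 and 3b if still eligible". A counting rule is missing, but Table 4 shows 105 + 105 = 210, with no sign of double counting.

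**Conclusion.** The concern holds for the proportion analysis only. Deleting subjects censored before the last planned day makes selection depend on outcome. At background 0.7 with equal dropout at the plan's annual rates over 182 days, VE is understated by about 0.6 to 1.2 points at HR 0.55 and 0.7 to 1.4 points at a 45% risk reduction. It would be up to about 3 points if all that dropout fell within follow-up. Unequal dropout would then move it from about -5 points to slightly positive. These sizes rest on constant hazards and dropout independent of infection; earlier infection enlarges the bias, later infection shrinks it, and informative dropout is not covered. The conclusion of the primary efficacy analysis is not threatened by this rule.

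Separately, ITT lacks a stated membership and time origin. That is a gap in definition affecting few main-phase subjects, not evidence that randomised subjects will be excluded.

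**What to change.** In Section 13.1.2, replace the deletion rule. Estimate each arm's cumulative infection probability at the last planned day from the interval-censored survival estimate, so that censored subjects contribute until they leave, and base the proportion VE on the ratio of these probabilities. Keep the exact test on completers as a sensitivity analysis, with completers defined by follow-up to the last planned day whatever their smear results.

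Add a short definition of ITT for each phase. In the main phase, give a randomised subject who misses the 3rd injection the scheduled date of that injection as time origin, and count each subject once. In the booster phase, restrict ITT to subjects enrolled in that phase. Those who do not enrol are complete and unblinded at Day 295 or 211 (Sections 4.4 and 11.14), so an origin at the 4th injection has no meaning for them.

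The cost is a few sentences and a small change in programming. The interval-censored method is already planned, and no added subjects, visits or samples are needed.

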13.1.3 Immunogenicity analysis

We will characterize and compare immunogenicity responses between vaccine and placebo arms by Wilcoxon rank sum test or two-sample t-test after proper transformation. We will also compare the immunogenicity response before and after vaccination by Wilcoxon signed rank test or paired t-test after proper transformation. Figures of immune responses in each study arm will be provided to depict the pattern of change in immune responses.

We will explore the impact of PfSPZ Vaccine on the genotype and transcriptome profile of parasites isolated from study subjects using a linear regression or a generalized linear regression.

The same immunogenicity analysis will be carried out at the end of the main phase and the end of the booster phase.

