Controls from 14-I-N010 (N = 44) are also included. Assay was performed on serum drawn following the third vaccine dose. The Malians had significantly lower responses, with many giving negative results (i.e., lower OD 1.0 following the third dose than prior to the first vaccination). Green dots represent volunteers who were protected against CHMI or natural exposure; red dots represent volunteers who were not protected.

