3 STUDY DESIGN

This study will enroll healthy Malian adults between 18 and 35 years of age to participate in a randomized double blind, placebo-controlled study to assess the safety, immunogenicity and protective efficacy of boosting during the second transmission season. Participants will be immunized with a 3-dose series of 9×10^5 PfSPZ Vaccine (cryopreserved radiation attenuated *P. falciparum* sporozoites via DVI) at 0, 8 and 16 weeks interval or 0, 1 and 4 weeks starting during the dry season (see [Figure 5](#)). Vaccinated subjects and controls will then be assessed for malaria infection during the ensuing malaria transmission season. Volunteers will be randomized into four arms. Arms 1 and 3a will be randomized first in a 2:1 ratio. Arms 2 and 3b will be randomized into a 2:1 ratio a few weeks later.

At the completion of the follow up phase after the primary series, participants who received all three vaccine doses and are still enrolled in the study will be invited to continue participation in the study to receive a booster vaccine dose. This 4th dose will be administered prior to the beginning of the following transmission season, approximately 10 months post the 3rd vaccination. Those enrolled in the vaccine arms (*Arms 1 and 2*) will receive one injection of 9×10^5 PfSPZ while those participants enrolled in the control arms (*Arms 3a and 3b*) will receive one injection of normal saline. The study will be maintained blinded as the participants transition from the main phase to the booster phase. Vaccinated subjects and controls will then be assessed for malaria infection during the ensuing malaria transmission season.

Figure 5: Study Schema

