4.3 Exploratory Endpoints

Immunogenicity:

- Measurement and comparison of various immunological parameters:
 - in the same subject prior to and after vaccination
 - between parasitemic and aparasitemic subjects
- Determination of the genotype of parasites isolated from study subjects, using microsatellite typing, sequencing, and/or SNP chip assays.

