4.4 Sample Size and Estimated Duration of the Study

A total of 210 volunteers will be enrolled/randomized in this trial, 70 subjects in each arm vaccine arms (Arm 1 and 2) and 35 subjects in each control arms (Arm 3a and 3b). A total of 140 subjects will receive PfSPZ Vaccine and 70 will only receive placebo.

Definitions for the purpose of this study:

- **Screened** – subjects will receive a study screening number when the informed consent is signed and will either be determined as “eligible” or “screen failure” as noted below.
 - Screening may be completed over the course of multiple visits.
 - Screening, in most cases, will occur within 56 days prior to administration of vaccine #1.
 - If the screening visit is >56 days administration of vaccine #, then an updated medical review and laboratory testing (CBC, ALT, Creatinine, ECG, Urinalysis, Pregnancy test (for females) will be completed to determine eligibility for enrollment.
 - **Note:** HIV, Hepatitis B, Hepatitis C and ECG are to be repeated during booster phase screening **ONLY IF** clinically indicated
- **Eligible** - subjects will be considered eligible to enroll once they have completed the screening procedures and have **met all inclusion** and **not met exclusion** criteria.
- **Screen Failure** – subjects are considered screen failures when they meet one of the following criteria after signing consent:
 - Screening results reveal that the subject is ineligible.
 - Subject withdraws consent before being vaccinated and/or randomized.
 - Subject cannot present to clinic for enrollment prior to study completing enrollment.
 - Subject is determined eligible for enrollment after study completes enrollment.
- **Randomized** – the subjects are considered randomized when they meet the following criteria:
 - Meet eligibility criteria.

- Study identification number (ID) assigned.
- Randomization number assigned.
- **Enrolled** – In the main phase, subject will be considered enrolled beginning with the collection of baseline labs on study Day -14.
 - In the booster phase, subject will be considered enrolled beginning with the receipt of artemether/lumefantrine prior to receiving 4th vaccination
 - Subjects enrolled in main phase but have not received the first vaccination may be replaced up to the accrual ceiling set for the study.
- **Discontinued/Withdrawn** – subjects are considered discontinued when they meet one or more of the following criteria:

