Appendix A: Clinic and Laboratory Procedures For Arms 1 & 3a - Booster (Vaccination # 4)																								
		Clinic visits	1	2	3	4	5	6	7	8	9	10	11	12	13	14	15	16	17	18	19	20	Unscheduled -- Blood Smear Positive	
		Study Day	323	351	362	372	379	380	382	386	393	407	421	435	449	463	477	491	505	519	533	561	N/A	
		Days post-PfSPZ Vac #4	-56	-28	-17	-7	0	1	3	7	14	28	42	56	70	84	98	112	126	140	154	182	N/A	
		Weeks post-PfSPZ Vac #1	46	50			54					58		62		66		70		74		80	N/A	
		Visit windows (days)	-14/+21	-14/+21	-7/+2	±3	-7/+14	+1	+1	±2	±3	±3	±5	±5	±5	±5	±5	±5	±5	±5	±5	±5		
		Clinic f/u		Booster Screen	AL	Safety F/U	PfSPZ Vac #4 ¹	Safety F/U	Safety F/U	Safety F/U	Malaria F/U	Malaria F/U	Malaria F/U	Malaria F/U	Malaria F/U	Malaria F/U	Malaria F/U	Malaria F/U	Malaria F/U	Malaria F/U	Malaria F/U	Unblinding visit	Unscheduled Visit Positive BS	
CLINICAL PROCEDURES																								
		Complete medical history/physical		X																				
		Malaria Comprehension Exam		X																				
		Pre-test/Post-test HIV counseling ²		(X)																				
		Pregnancy Prevention Counseling		X	X	X	X	X	X	X	X	X	X	X	X	X	X	X	X	X	X	X	X	
		Interim clinical evaluation	X		X	X	X	X	X	X	X	X	X	X	X	X	X	X	X	X	X	X	X	
		AE/SAE assessment	X	X	X	X	X	X	X	X	X	X	X	X	X	X	X	X	X	X	X	X	X	
		Conmed review	X	X	X	X	X	X	X	X	X	X	X	X	X	X	X	X	X	X	X	X	X	
		AL dose			X																			
		PfSPZ Vaccine (Arm 1 only) ¹					X																	
LABORATORY PROCEDURES																								
		Screening/Safety Labs and procedures																						
		CBC with differential	MRTC CAP lab/1UR/1PD	EDTA	2		2		2		2		2		2		2		2		2			
		ALT, Cr		SST	3		3		3		3		3		3		3		3		3			
		Hepatitis B, C, HIV testing ²		SST	(5)																			
		Urine dipstick or UA		Urine Container																				
		Urine/Serum Pregnancy Test (females only)		Urine Container or Lithium Hep																				
		ECG ²	NIH/Mali Cardio	N/A	(X)																			
Malaria Infection Assays																								
		qPCR	MRTC CAP lab/LMIV	EDTA	0.5	0.5	0.5	0.5	0.5	0.5	0.5	0.5	0.5	0.5	0.5	0.5	0.5	0.5	0.5	0.5	0.5	0.5	0.5	
		Peripheral Blood Smear		EDTA	0.5	0.5	0.5	0.5	0.5	0.5	0.5	0.5	0.5	0.5	0.5	0.5	0.5	0.5	0.5	0.5	0.5	0.5	0.5	
Research Assays																								
		Humoral Assays	MRTC/LMIV	SST	10	5					5	2.5				2.5				2.5				
		Cellular Assays ³		NaHep	10	10			10		10	10			10					10				
		Ex Vivo Assays		EDTA		0.5					0.5				0.5					0.5				
		Parasite Purification (CF11)		EDTA																			(4)	

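### The vaccine-placebo comparison of immune responses names no baseline adjustment: an avoidable loss of precision on an exploratory objective, of a size the documents do not fix

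*Combined protocol and SAP*

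**What the plan says.** Section 13.1.3 of the combined protocol and SAP gives two separate analyses. Between arms, the plan is to "compare immunogenicity responses between vaccine and placebo arms by Wilcoxon rank sum test or two-sample t-test after proper transformation". Within subjects, it is to "compare the immunogenicity response before and after vaccination by Wilcoxon signed rank test or paired t-test after proper transformation". Baseline adjustment, change score and stratum term are not mentioned for the between-arm test, and the response variable is not formally defined.

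Pre-vaccination measurement is part of the design. Section 4.3 lists, as an exploratory endpoint, immunological parameters compared "in the same subject prior to and after vaccination". Section 7.2 ties main-phase enrolment to "collection of baseline study samples on study Day -14". The Appendix A booster schedules list "Humoral Assays" and cellular assays at visits before dose 4.

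On size and allocation, section 4.4 gives "70 subjects in each arm vaccine arms (Arm 1 and 2) and 35 subjects in each control arms (Arm 3a and 3b"), and section 3 states that "Arms 1 and 3a will be randomized first in a 2:1 ratio". Section 13.3 stratifies randomisation by village. Immunogenicity is exploratory in sections 2.3 and 4.3.

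**The concern.** In a randomised comparison of a continuous outcome that was also measured before treatment, the baseline value usually explains part of the between-subject spread. A two-sample test leaves that part in the error term. The participants here are malaria-exposed adults, so they may differ in malaria-specific immunity before any dose. Section 1.4.3.1 describes only modest antibody responses to circumsporozoite protein (CSP) in the earlier Mali trial. A modest signal is the case in which extra precision is worth having, and each regimen has only 35 controls.

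The within-subject test does not fill the gap. Section 1.7 places the main-phase doses between June and September 2018. Section 6.1 places transmission from June to December, and section 8.6 includes assays against blood-stage antigens. Natural exposure could therefore move responses in both arms between the two samples. The vaccine-placebo contrast is the one that isolates the vaccine, and it is the one with no stated use of baseline.

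**Working it through.** **No figure to reproduce.** Section 13.2 sizes the trial mainly on vaccine efficacy. The documents give no power, SD, effect size or pre/post correlation for any immune assay.

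**Inputs from the documents.** Each regimen has 70 vaccine and 35 placebo subjects (section 4.4), or 140 and 70 if regimens are pooled. Annual drop-out is 15% to 28% (section 13.2). That leaves about 60 and 30 (70 × 0.85 = 59.5; 35 × 0.85 = 29.75) or about 50 and 25 (70 × 0.72 = 50.4; 35 × 0.72 = 25.2).

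**Assumptions.** Two-sided 5% tests; SD of 1 on the transformed scale, equal before and after vaccination; r from 0.3 to 0.7.

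**Is a pre-dose-4 sample drawn?** Column positions in the booster table have to be inferred, and the daily totals allow it. At day -28: 2 + 3 + 0.5 + 0.5 + 10 + 10 + 1 = 27 mL, matching the printed 27 with humoral and cellular draws of 10 mL each. At day -17: 0.5 + 0.5 + 5 + 10 + 0.5 + 1 = 17.5 mL, matching the printed 17.5 with humoral 5 mL and cellular 10 mL.

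**Variance of the arm difference, relative to post-vaccination levels alone:**

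- levels alone: 1
- change score: 2(1 - r)
- ANCOVA: 1 - r²
- ANCOVA relative to change score: (1 - r²) / [2(1 - r)] = (1 + r)/2

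| r (assumed) | change score | ANCOVA | ANCOVA / change score |
|---|---|---|---|
| 0.3 | 1.40 | 0.91 | 0.65 |
| 0.5 | 1.00 | 0.75 | 0.75 |
| 0.7 | 0.60 | 0.51 | 0.85 |

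**What this means for 70 versus 35.** The standard error of the unadjusted difference is √(1/70 + 1/35) = 0.207 SD. The normal approximation for 80% power gives (1.96 + 0.84) × 0.207 = 0.580 SD; the noncentral t gives 0.585 SD. Fix the true difference at 0.585 SD:

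| r | power, levels | power, change score | power, ANCOVA | total N for levels to match ANCOVA (105 / factor) | ANCOVA difference at 80% power (0.585 × √factor) |
|---|---|---|---|---|---|
| 0.3 | 80% | 65.8% | 83.6% | 115 | 0.558 SD |
| 0.5 | 80% | 80.0% | 89.9% | 140 | 0.507 SD |
| 0.7 | 80% | 95.1% | 97.5% | 206 | 0.418 SD |

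Other arm sizes keep the same proportions. At r = 0.5 the detectable difference falls from 0.695 to 0.602 SD for 50 versus 25, and from 0.412 to 0.357 SD for 140 versus 70.

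**Check by simulation** (4,000 runs per setting, 70 versus 35, difference 0.59 SD). At r of 0.3, 0.5 and 0.7, power was 79%, 80% and 79% for the rank-sum test; 81%, 82% and 80% for the t-test; and 85%, 90% and 98% for ANCOVA. Type I error was between 4.4% and 5.3% for every method, so the planned tests are valid and merely less precise.

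**The case against.** **Response may already mean change from baseline.** Section 1.4.3.1 reports the CSP ELISA as net OD 1.0 and describes Malian subjects "with many giving negative results (i.e., lower OD 1.0 following the third dose than prior to the first vaccination"), which is a baseline-referenced usage. Section 13.1.3, by contrast, speaks of the response before and after vaccination, which reads as a level at one time point. The text does not settle it, so both comparisons are shown above. The objection changes the size of the gain: at r = 0.7 it shrinks from about twice the subjects (1/0.51) to about 18% more (1/0.85). It does not remove the gain, since ANCOVA is never less precise than a change score under the stated assumptions.

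**Baseline may explain little.** A reader might infer from the post-below-pre results that baseline drives much of the spread. That does not follow. Such results also fit a weak response plus assay noise, which would mean a low correlation. They come from one assay in one earlier trial. Pre-existing immunity is described only qualitatively, with no titres or SDs. This part of the objection stands, and r may differ by assay.

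**Randomisation already covers chance imbalance.** This is correct. A reader might infer that baseline imbalance biases the arm difference. It does not: the planned test's error rate already allows for it.

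**The main-phase baseline is partly inferred.** The Appendix A tables in the text available cover the booster phase only, and section 7.2 does not say which assays the Day -14 samples serve. Section 4.3 nevertheless requires a pre-vaccination value.

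**Adjusting for the pre-dose-4 value could mislead.** This stands too. The value is measured after three randomised doses and may carry the primary-series effect, so it cannot be treated as an ordinary baseline.

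**One log-linear model may not suit every assay.** This is fair for assays with many zero or undetectable values, and the fix allows for it.

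**Conclusion.** The point holds as a minor improvement. Section 13.1.3 names no use of baseline in the vaccine-placebo comparison, although the design provides for pre-vaccination measurement. The consequence is lost precision on an exploratory objective. It is not a bias, and it does not touch the safety or efficacy analyses.

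The size is a range resting on an assumed r. Against post-vaccination levels, the avoidable part of the variance is 9%, 25% or 49% at r = 0.3, 0.5 or 0.7, and it is trivial below about 0.2. Against change scores, it is 35%, 25% or 15% at the same values. The 1 - r² result applies to a baseline taken before randomised vaccination, so it supports adjustment for the pre-dose-1 value. It does not carry over to the pre-dose-4 value. The documents do not support a claim that the loss is large for any particular assay.

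**What to change.** Revise the between-arm sentence of section 13.1.3 along these lines:

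- **Main analysis.** Fit a linear model of the transformed (for example log) post-vaccination response on arm, the transformed pre-dose-1 value and village, the randomisation stratum. Report the adjusted ratio or difference with its confidence interval.
- **Assays with many zero or undetectable values.** Use a rank-based ANCOVA, and name these assays and the transformations in advance.
- **Sensitivity analysis.** Keep the rank-sum test, and state whether it is applied to levels or to changes.
- **Booster phase.** Use the pre-dose-1 value as the baseline for the total vaccine effect. Label any analysis adjusted for the pre-dose-4 value as the increment after boosting, and say that this value follows randomised vaccination and may carry the primary-series effect.

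The cost is a few sentences of analysis text, with no new samples or visits. The one thing to confirm first is which assays have a pre-dose-1 result, since the text available does not list them for the main phase.
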